5.1.2.4 Comorbid symptoms and potential moderators

Behavioral Inhibition System and Behavioral Activation System Scales (BIS/BAS;⁷⁵). The behavioral inhibition system (BIS) and behavioral activation system (BAS) scales are self-report measures used to examine a patient's inhibition and activation sensitivity. The scale is composed of four sub scales, one scale to measure BIS sensitivity, and three subscales related to BAS sensitivity (Drive, Fun Seeking, and Reward Responsiveness Scales). The BIS component measures patient sensitivity to signals of punishment, for example, patients high in BIS sensitivity are more responsive to punishment cues and experience greater negative affect (anxiety) in situations associated with punishment. The BAS component measures sensitivity to signals of reward, for example, patients with high BAS sensitivity are highly responsive to reward cues and experience positive affect. Internal consistency was high for the BIS ($\alpha=0.74$), BASS Reward Responsiveness ($\alpha=0.73$), BAS Drive ($\alpha=0.76$), and BAS Fun Seeking ($\alpha=0.66$). Recently, AN has been hypothesized to be related to abnormalities in reward processing. Adolescents will complete this about themselves; parents will complete it about themselves and their child.

Behavior Assessment System for Children-3 Parent and Child Version (BASC-3;⁷⁶). This is 139 item self-report measure that assesses affective and behavioral functioning in adolescents. The BASC-3 is well validated and has reliability ranging from .88-.97 with test-retest reliability of .81-.89. Both parent and self-report versions are available, allowing for comparison of parent and self observations of behavior. The measure includes both adaptive scales (e.g. Daily Living, Social Skills, Functional Communication) and clinical scales (e.g. Depression, Anxiety, Withdrawal, Atypically). Given that mood disorders and interpersonal deficits often accompany AN, a full assessment of these domains will allow broader based evaluation of treatment. It might also provide information regarding the adolescent's strengths and allow for tracking of improvement in adaptive areas.

Experience of Caregiving Inventory (ECI;⁷⁷). This 66-item self-report measure assesses caregivers' perception of their experiences interacting with their child. It includes subscales with both negative (eight subscales) and positive items (two subscales). This measure is included to assess change in parental experience of having an ill child (i.e. greater hope for positive outcome, less judgmental of the adolescent). The ECI has demonstrated good construct validity (explaining 36% of the variance in scores on measures assessing general health and coping) and high internal consistency (Cronbach's alphas ranging from 0.74 to 0.91) among caregivers for patients with AN.⁶⁹ It is only completed by parents.

Intolerance of Uncertainty (IUS;⁷⁸). The IUS is a 27 item self-report measure that assesses six aspects of intolerance to uncertainty, 1) the emotional and behavioral consequences of being uncertain, 2) how being uncertain reflects on an individual's character, 3) expectations that the future be predictable, 4) frustration surrounding unpredictability of the future, 5) attempts to control the future, 6) and all or nothing situations when in uncertain situations. Items are measured on a 5 point Likert scale. The IUS showed strong internal consistency ($\alpha = .94$) and good test-retest reliability ($r = .74$) over a 5 week period. The IUS is validated and considered to have good concurrent validity with measures of worry, anxiety, and depression. The IUS will be administered at all time points.

Obsessive Compulsive Inventory (OCI;⁷⁹). There is an adult (OCI) and child (C-FOCI) version of this measure. The C-FOCI is a 17 item self-report questionnaire that assesses presence of common obsessions and compulsions. There are two parts to this scale – a symptom checklist and a severity scale. The adolescent checks yes or no for the checklist and for the scale endorse items according to a range from 0 (none) to 4 (extreme). The internal consistency was acceptable for both parts ranging from .76-.79. OCD is highly comorbid with AN and can appear as rigid behavior. Parents will complete the OCI about themselves. This is an 18 item scale using a 5 point Likert type response that assesses distress associated with obsessions and compulsions. It has good internal consistency reliability (.81-.93). Parents will complete the OCI.

Detail and Flexibility Questionnaire (DFlex;⁸⁰). The DFLEX is a 24-item self report measure assessing cognitive rigidity and attention to detail, both considered aspects of neurocognitive functioning. Both aspects have been measured in an Autistic sample using the Autism Spectrum Quotient (AQ), and thus the AQ was used to determine construct validity. A strong correlation for cognitive rigidity was shown ($r = .72$) and a moderate correlation for attention to detail ($r = .26$). The DFLEX is a new measure developed to address both flexibility and central coherence. It will be completed by parents and adolescents.

Line Bisection Task (LBT;⁸¹). The LBT has been widely used as a behavioral measure of visual neglect in patients with brain damage. More recently, neuroimaging research has confirmed it can also be used to measure approach motivation in non-clinical populations. In the task participants mark the perceived mid-point of staggered horizontal lines of the same length in millimeters (mm). When participants make errors in marking the midpoint left of the true midpoint these are scored as negative. Meanwhile, positive scores mean greater left to right hemisphere activation. The LBT is being piloted in this study as a behavioral measure of approach-based coping. It will be completed by both adolescent and parents.

Family Questionnaire (FamQ;⁸²). Expressed emotion (EE) has traditionally been assessed via clinical interview, however the interview can be laborious and time consuming. In order to address this issue, the FQ was developed. It is a 20 item self-report measure that includes two subscales: criticism and emotional over involvement. Scores on the FQ have high convergent validity with more traditional interview assessments of EE. Test-retest reliability over two weeks produced Pearson correlations of $r= 0.84$ for the criticism (CC) and $r=0.91$ for the emotional overinvolvement (EOI) subscales. Similarly, internal consistency was good, ranging from 0.90-0.92 for the CC and 0.79-0.82 for the EOI subscales. Only parents will complete this measure.

Depression Anxiety Stress Scale (DASS;⁸³). The DASS is a 42-item self-report instrument measuring current symptoms of depression, anxiety, and stress on three separate scales. Higher scores on each of the scales indicate higher levels of depression, anxiety, and stress. Among clinical and community populations high internal consistency was found for the depression ($\alpha=0.94$), anxiety ($\alpha=0.87$), and stress subscales ($\alpha=0.91$). The DASS-21 has also been found to have good convergent reliability with other well validated measures of depression and anxiety (e.g., Beck Depression Inventory, State-Trait Anxiety Inventory). Parents and adolescents will complete this about themselves.

Eating Disorder Flexibility Index (EDFLIX): The EDFLIX is a 51-item questionnaire where participants use a six-point Likert scale to respond to each question. The EDFLIX ranges in

questions, some asking specifically about their eating disorder (e.g., “I need my meals to be predictable (time, food, content)” and “I prefer eating the same foods as I usually do”) and others are more abstract (e.g., “I find it difficult to get used to new situations” and “When I am stuck on a task, I am unable to come up with new solutions.”)

Autism Spectrum Quotient (AQ-10): The AQ is a 10-item questionnaire for parents to complete regarding the child’s behavior if their child is between 12 and 15 years old. If the child is 16-18 years old, the child will complete this questionnaire about themselves. Additionally, parents will complete this questionnaire about their own behavior. The AQ contains a 4-point scale, ranging from “definitely agree” to “definitely disagree.” There are two versions of this questionnaire, one for participants aged 12-15 years old and another for participants aged 16 and older. Examples of questions are, “S/he notices patterns in things all the time” and “S/he is good at social chit-chat.”

Social Reward Questionnaire (SRQ): There are two versions of the SRQ, one for adults and one for adolescents. We will administer the SRQ designed for adolescents (SRQ-A). This 20-item questionnaire is scored on a 7-point scale, with responses ranging from “Strongly disagree” to “strongly agree.” The questionnaire asks participants to rate different statements such as, “I enjoy treating others fairly” and “I enjoy keeping promises I make to others.”

Parent Versus Anorexia Scale (PVA): The PVA is a 7-item questionnaire for parents to complete regarding their own self efficacy to feed their adolescent. They respond to each item on a 5 point Likert scale ranging from “strongly disagree” to “strongly agree”. It is aimed at measuring parental efficacy throughout family-based treatment to track changes over time.

Treatment Credibility/Alliance

Credibility/Expectancy Questionnaire (CEQ;⁸⁴) This 6-item questionnaire measures both cognitive and affective elements regarding how much individuals believe in, and expect they will improve, due to treatment. The CEQ was designed to be used in clinical outcome trials and was validated on a mixed sample of patients. It has good internal consistency (.85) and test-retest reliability (.75-.82).

Working Alliance Inventory (WAI;⁸⁵) The WAI is a 36 item measure that assesses goals, tasks, and the bond present in therapy. It can be completed by the therapist, client, or an observer. Reliability ranges from .89-.93. Therapeutic alliance is recognized as an important contributor to outcome, however, adolescents with AN have been reported to demonstrate deficits in forming a strong therapeutic relationship and this may impact outcome.

CRT Treatment Evaluation Questionnaire (TEQ;⁸⁶) The TEQ is a 20-item measure that assesses how participant feel about CRT, including the perception of change, view of the therapist, treatment satisfaction. It is completed at the end of treatment and will only be completed by the individuals who receive CRT. It currently does not have published reliability statistics as it is a relatively new measure.

5.2 Efficacy Evaluations

There is no efficacy evaluation. The purpose of this study is to determine whether or not CRT can improve flexibility in the parents or the adolescent. We will gather data on efficacy in future work.

5.3 Safety Evaluation

Subject safety will be monitored by adverse events, weight, parental report of behavior, and weekly checks on eating disorder symptoms (EDE short version). Regular contact with the adolescents' pediatricians will also occur. When questions may arise about adolescent health, [name] will review vital signs, weight gain, and eating disorder symptoms and make recommendations vis a vis hospitalization or referral to a higher level of care.

6 STATISTICAL CONSIDERATIONS

6.1 Primary Endpoint

Aim 1: To identify whether or not it more impactful to add a parent or adolescent component of CRT to standard FBT. To assess if CRT engages the target, we will use mixed 3 (treatment) x 2 (time) Multivariate Analysis of Covariance (MANCOVA): one for adolescents, one for mothers, and one for fathers. The covariate for all analyses is total IQ on the WASI. Dependent variables are as follows: Trails Number-Letter Sequencing, Inhibition, Inhibition/Switching, Correct Response Shifting, Category Switching, or Description 1 or 2 and Shift on the BRIEF-2. We will follow these steps:

1. Conduct omnibus MANCOVA and evaluate significance. If not significant, stop and move to next analysis.
2. If the omnibus test is significant, we will conduct individual 2 (treatment) X 2 (time) Analysis of Covariance (ANCOVA) to determine which dependent variable had significant change, with IQ again as the covariate.
3. Each assessment of the target (DV) will be examined. Results will inform the Go/No-Go Decision as described in Table 6.

These three steps will be repeated for adolescents, mothers, and fathers. We will include all three groups in the initial MANCOVA and follow-up with planned comparisons (ANCOVA) of FBT vs the appropriate CRT condition. In all analyses, we will focus on the within and between-group effects, examining interaction effects are not necessary to evaluate the target. As we have chosen measures demonstrated to change with CRT,^{40,87-90} we will maintain $\alpha=0.15$ for each analysis.⁹¹ We do not expect adolescents whose parents receive CRT or parents whose adolescents receive CRT to demonstrate increases in flexibility. However, should the planned ANCOVAs not be significant, we will be able to explore other possible group differences. Additionally, we will explore the relationship between dependent variables via discriminant analysis. These additional methods to examine the data will not factor into the Go/No-Go decision, but will enhance the depth of our understanding of the data and contribute to our understanding of neurocognition in AN.

Aim 2: To determine the dose of CRT needed to lead to a medium effect size. Some research indicates that ≥ 8 sessions of CRT are necessary for improvement in cognitive flexibility with AN.⁹² It is unknown how many sessions will be needed for significant change in parents of

adolescents with AN. To determine optimal dose, we will model change across the 15 sessions using latent growth curve modeling (LGCM). LGCM will allow us to analyze individual and average trajectory and model linear and quadratic trend. We will visually assess for the point (dose) at which there is a significant decrease in the *rate* of improvement (quadratic). Parameter estimation will employ Maximum Likelihood (ML) estimation.^{93,94} We will evaluate model fit using chi-square (χ^2), Comparative Fit Index (CFI), Standardized Root Mean Squared Residual (SRMR), and Root Mean Squared Error of Approximation (RMSEA).⁹⁵ The following values are indicative of acceptable fit between the model and the observed data variance/covariance matrixes: CFI, SRMR, and RMSEA, $< .95$, $< .80$, and $< .05$, respectively. We will assess and compare different models using BIC and novel criteria such as Scaled Unit Information Prior BIC.^{96,97} Examining standardized model residuals in addition to global fit indices (GFI) permits us to identify model misspecification even if GFI values suggest adequate fit.⁹⁵

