2.1 Primary Objective (or Aim)

Aim 1: To identify whether or not it more impactful to add a parent or adolescent component of CRT to standard FBT. We hypothesize that both adolescents and parents who receive CRT will have greater increases in cognitive flexibility than those who receive FBT alone. We will examine magnitude of change in cognitive flexibility across groups.

Aim 2: To determine the dose of CRT needed to lead to a medium effect size (increase in cognitive flexibility). We will examine the dose of CRT needed to obtain an increase in cognitive flexibility equal to a medium effect.

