6.4 Sample Size and Power

Power analysis Aim 1. In the initial phase of the proposed project (R61), our sample size estimation is based on a mixed MANCOVA design with two repeated measures from baseline to end-of-treatment (EOT; within subjects component) and three groups (CRT_P, CRT_A, and FBT; between subjects component). Based on a review of the literature, we are powering for a medium effect size. Our effect size estimate is Cohen's f statistic.⁹⁸ This effect size estimate is a ratio of variation explained to that unexplained by the model (treatment groups), and is expressed as

follows: $f = \sqrt{\frac{\eta^2}{(1-\eta^2)}}$, where $\eta^2 = \frac{\sigma_{model}^2}{\sigma_{Total}^2}$; proportion of variability due to the model.^{99,100}

Heuristics for small, medium, and large effect sizes are .1, .25, and .4, respectively. We selected an alpha of 0.15, given the nature of the study and the difficulty in recruiting participants from a low prevalence condition. Alpha of 0.15 is essential to provide adequate power for this study.⁹¹ As any analysis powered for a medium effect will also be powered for a large effect, we only highlight the expected medium effect. For all analyses, we specified an $\alpha=0.15$, two time points, and a correlation between measures of .3 (based on unpublished data). The anticipated N accounts for dropouts (i.e., number enrolled will be higher).

Power analysis Aim 2. Using Mplus 7.2,⁹⁴ we conducted a LGCM Monte Carlo simulation with 1000 replications^{94,101-103} to determine power to identify CRT_{P/A} dosage based on a half standard

deviation increase (rate of change; slope) from baseline (effect size) above FBT. With 15 participants in 3 groups across 5 time points, parameter and standard error bias were $\leq 5\%$, confidence interval coverage $\geq 90\%$, and power = 0.59.

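### Aim 1 never adjusts an outcome for its own baseline: at the plan's r = .3 the difference-in-change contrast has about 1.5 times the variance of a baseline-adjusted ANCOVA, and the between-group effect the plan says it will read does worse

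*Combined protocol and SAP*

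**What the plan says.** Section 6.1 gives the omnibus model, run separately for adolescents, mothers and fathers: "we will use mixed 3 (treatment) x 2 (time) Multivariate Analysis of Covariance (MANCOVA"). If it is significant, each outcome goes to "individual 2 (treatment) X 2 (time) Analysis of Covariance (ANCOVA"), comparing FBT with the relevant CRT arm. If it is not, that analysis stops.

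On adjustment, section 6.1 says "The covariate for all analyses is total IQ on the WASI". Section 6.4 identifies the two levels of time by describing a "mixed MANCOVA design with two repeated measures from baseline to end-of-treatment". So each outcome's baseline score is on the outcome side at both steps.

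On which effect is read, section 6.1 says: "In all analyses, we will focus on the within and between-group effects, examining interaction effects are not necessary to evaluate the target". The hypothesis in section 2.1 is that "both adolescents and parents who receive CRT will have greater increases in cognitive flexibility than those who receive FBT alone".

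For planning, section 6.4 uses a medium effect (f = .25), "two time points, and a correlation between measures of .3 (based on unpublished data"), and a relaxed significance level: "We selected an alpha of 0.15, given the nature of the study". Section 3.3.2 expects about 60 enrolled and at least 45 evaluable. The Aim 2 power text uses 15 per group.

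**The concern.** The arms are randomised, and Table 1 schedules the D-KEFS and BRIEF-2 at intake. Using each baseline score as a covariate is the standard way to gain precision in that setting. Using it as a second outcome gains less and, when the correlation is below 0.5, gives a noisier treatment contrast than ignoring baseline altogether.

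IQ does not replace this adjustment. It enters as one value per person, so it sharpens a difference-in-change contrast only to the extent that it predicts change.

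This matters because the trial is small and the plan raises alpha to 0.15 to obtain adequate power. Sections 6.1 and 10 tie the Aim 1 results to a Go/No-Go decision on the second phase. The plan accepts more false positives to gain power while leaving available precision unused.

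**Working it through.** **Inputs.** r = .3, alpha = .15 and f = .25 are from section 6.4. The figure of 15 per arm is 45 evaluable over three arms, and is also in the Aim 2 power text.

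**Assumptions.** r is each outcome's baseline to end-of-treatment correlation. The SD is equal at both times and set to 1. IQ is ignored. Tests are two-sided.

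**The plan's own figure.** The supplied text states no Aim 1 power, so there is none to reproduce. From the plan's inputs at N = 45, repeated-measures noncentral F gives 0.64 for the between-group effect (lambda = f² × N × 2/(1 + r)), 0.91 for the within-group effect and 0.85 for the interaction (both lambda = f² × N × 2/(1 − r)). The documents do not say which effect set the sample size.

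**Variance per subject for a net end-of-treatment difference d, at r = .3**

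- Treatment by time (difference in change): 2(1 − r) = 1.40.
- End-of-treatment score alone, baseline ignored: 1.00.
- End-of-treatment score adjusted for its baseline: 1 − r² = 0.91.
- Between-group main effect: the mean of the two scores has variance (1 + r)/2 = 0.65. Because baseline carries no treatment effect, it estimates only d/2. On the scale of d the variance is 4 × 0.65 = 2.60.

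**Ratios to the baseline-adjusted analysis**

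- Change: 1.40/0.91 = 1.54, which in general is 2/(1 + r).
- Between-group main effect: 2.60/0.91 = 2.86.
- Over r, the change ratio is 1.82 at .1, 1.33 at .5 and 1.18 at .7.

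At 1.54, the change contrast would need about 15 × 1.54 = 23 per arm to match 15 per arm with adjustment.

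**Small-sample correction.** With two arms of 15, estimating the baseline slope multiplies the ANCOVA variance by about 1 + 1/26. The change ratio becomes 1.54/1.038 = 1.48. Simulation of 20,000 trials at 15 per arm gave 1.48 for change and 2.77 for the rescaled main effect.

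**Illustrative power.** This is one FBT-versus-CRT test with no omnibus gate, 15 per arm, by noncentral t with SE = √(2/15 × variance). There are 28 df, or 27 for the adjusted analysis, which includes the slope cost. The main effect is tested as d/2 with variance 0.65.

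| Net difference d | Change | Between-group main effect | Baseline-adjusted |
|---|---|---|---|
| 0.5 SD | 0.39 | 0.28 | 0.48 |
| 0.8 SD | 0.65 | 0.46 | 0.78 |
| 1.0 SD | 0.80 | 0.59 | 0.91 |

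**Link to the planning effect.** If only one arm responds, the 3 × 2 interaction has f = d/√18, so f = .25 corresponds to d = 0.25 × 4.243 = 1.06 SD. Power there is 0.83 (change), 0.63 (main effect) and 0.93 (adjusted).

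**The case against.** **The 1.54 belongs to a test the plan sets aside.** This is correct. Section 6.1 says interactions need not be examined, so a reader should not infer that the planned test loses 54%. The figure applies to the contrast that answers the section 2.1 hypothesis. The between-group effect the plan does name loses more, and the within-group effect cannot compare CRT with FBT. Which effect is tested has to be settled together with how baseline is used.

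**The model is not wrong.** Also correct. Under randomisation the difference-in-change contrast is unbiased. A reader might infer that Aim 1 is invalid, but the documents support only a loss of precision.

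**The power figures are not the trial's power.** They are for a single two-arm test without the omnibus gate or IQ, at illustrative effect sizes. They rank the estimators and do not show that Aim 1 is underpowered. No Aim 1 power is stated to contradict, and at the planning effect the change contrast already has 0.83.

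**r is uncertain.** Section 6.4 gives one unpublished value for several outcomes and three kinds of respondent, and its wording does not say that it is the correlation over time. The size of the gain depends on r. Its direction in large samples does not, because 2/(1 + r) exceeds 1 for every r below 1.

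**The effect on the decision cannot be seen.** Section 6.1 refers to Table 6 for the Go/No-Go rule, which is not in the supplied text. If that rule rests on within-group change or effect size, power for this contrast may matter less.

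**Conclusion.** The point holds as an available gain in precision. Under sections 6.1 and 6.4 no Aim 1 outcome is adjusted for its own baseline. At r = .3 the difference-in-change contrast has 1.54 times the large-sample variance of the adjusted analysis, or about 1.5 times at 15 per arm. This falls to 1.33 at r = .5 and 1.18 at r = .7. The between-group main effect has 2.86 times the variance at r = .3.

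For differences of 0.5 to 1.0 SD, adjustment raises single-test power by about 0.09 to 0.13 over change and by about 0.20 to 0.32 over the main effect. These figures rest on equal SDs, on r being the correlation over time, and on ignoring IQ and the omnibus gate. The change should be made, but the plan is not invalid without it.

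**What to change.** In section 6.1, remove the time factor at both steps.

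1. **Omnibus test.** Use a MANCOVA of the end-of-treatment scores on arm, with the outcomes' baseline scores and baseline WASI IQ as covariates. To save degrees of freedom, use a multivariate mixed model with baseline means constrained equal across arms. Changing only the follow-ups would leave the step that can stop the analysis on the less efficient model.
2. **Follow-up tests.** For each outcome, use an ANCOVA of the end-of-treatment score on arm, that outcome's own baseline and baseline IQ. Keep all three arms in the model and take FBT versus the relevant CRT arm as the contrast. Specify the intake IQ, because Table 1 repeats the WASI at the end of treatment.
3. **Effect of interest.** Delete the sentence saying interactions need not be examined, or replace it with this contrast.
4. **Power.** In section 6.4, state the Aim 1 power for this model, define r as the baseline to end-of-treatment correlation, and show a range for it.

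The cost is SAP wording, one degree of freedom per follow-up model, and several more in the omnibus test if every baseline score enters as a covariate. No new data are needed.

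### Section 6.1 does not say how WASI IQ is coded; if it is entered as recorded, the time test in the repeated-measures models refers to change at an IQ of zero, not average change

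*Combined protocol and SAP*

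**What the plan says.** Section 6.1 (Primary Endpoint, Aim 1) plans a mixed MANCOVA with three treatments and two time points, run separately for adolescents, mothers and fathers. A two-treatment by two-time ANCOVA per score follows if the omnibus test is significant. On the covariate it says only "The covariate for all analyses is total IQ on the WASI". The follow-up ANCOVAs are meant "to determine which dependent variable had significant change, with IQ again as the covariate".

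On which effects will be read, it says: "In all analyses, we will focus on the within and between-group effects, examining interaction effects are not necessary to evaluate the target". The time effect is therefore one of the two kinds of effect on which Aim 1 rests, and the results feed the Go/No-Go decision.

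The section is silent on three things: whether IQ is centred, whether an IQ x time term is fitted, and which IQ assessment is used. Sections 4.1 and 4.2.5 list IQ testing both at intake and at the end-of-treatment visit (Visit 18).

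**The concern.** In a repeated-measures (M)ANCOVA one between-subject design, here group and IQ, is applied to every within-subject contrast. With two time points that contrast is end of treatment minus baseline. IQ therefore enters the model for change even if nobody lists an IQ x time term, and the time test is the test of the intercept in the regression of change on group and IQ.

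An intercept is the prediction where the covariate equals zero. With effect-coded groups and mean-centred IQ, that is average change at average IQ. With IQ as recorded, it is change extrapolated to IQ 0, many standard deviations outside any sample. The question the plan wants answered is whether flexibility changed on average. The question tested would be whether a far-extrapolated line passes through zero.

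Two analysts could both follow Section 6.1 and reach opposite conclusions about the time effect from the same data, because of a coding choice the plan leaves open. If IQ is positively related to improvement, the extrapolated change is also shifted downwards, so a significant time effect need not mean improvement.

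**Working it through.** **Inputs from the documents.** Section 6.4 gives alpha ("We selected an alpha of 0.15, given the nature of the study"), two time points, a correlation of .3 between measures, and a medium effect ("Heuristics for small, medium, and large effect sizes are .1, .25, and .4, respectively"), so f = 0.25. With two time points, f = 0.25 for time means the two means lie 0.25 SD either side of their average, a change of 2 x 0.25 = 0.5 SD. Section 3.3.2 gives 45 evaluable families. Section 6.4 gives 15 per group for Aim 2, so FBT against one CRT arm is 30.

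**Assumed, not in the documents.** IQ mean 100-110, IQ SD 10-15, and the correlation of IQ with change.

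**The plan's own figure.** The text available gives no Aim 1 power. The 0.59 in Section 6.4 is for the Aim 2 growth model and has no bearing here. The benchmark is therefore the time-test power that the plan's own inputs imply.

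**Step 1: centred IQ.** The variance of change, in units of the score variance, is 2(1 - .3) = 1.4. The noncentrality is N x 0.5² / 1.4.
- N = 30: 30 x 0.25 / 1.4 = 5.36, power 0.797.
- N = 45: 45 x 0.25 / 1.4 = 8.04, power 0.913.

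**Step 2: IQ as recorded, unrelated to change.** The variance of the intercept is multiplied by 1 + (mean/SD)², and the noncentrality is divided by the same factor. For N = 30:

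| IQ mean / SD | Factor | Noncentrality | Power |
|---|---|---|---|
| 100 / 15 | 45.4 | 0.118 | 0.17 |
| 110 / 15 | 54.8 | 0.098 | 0.17 |
| 100 / 10 | 101 | 0.053 | 0.16 |
| 110 / 10 | 122 | 0.044 | 0.16 |

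Power is barely above alpha. With no average change, the rejection rate remains exactly 0.15.

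**Step 3: IQ as recorded, no average change, IQ correlated ρ with change.** Write R = mean/SD. The extrapolated change is -ρ x √1.4 x R, and the noncentrality is N x ρ²/(1 - ρ²) x R²/(1 + R²). For N = 30 and R = 100/15:
- ρ = .2: 30 x 0.04/0.96 x 0.978 = 1.22, rejection 0.37.
- ρ = .3: 30 x 0.09/0.91 x 0.978 = 2.90, rejection 0.59.

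These closed forms hold the sample IQ mean and SD fixed. Simulation that lets IQ vary between samples gives 0.35-0.36 and 0.56-0.57. With centred IQ the simulated rate is 0.15-0.17.

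**Step 4: omnibus test.** Simulation with 45 people and seven scores, assuming a correlation of .3 among the scores, gives power 0.17 for IQ as recorded against 0.96 centred. Rejection with no average change is 0.44 (ρ = .2) and 0.73-0.74 (ρ = .3), against about 0.16 centred. These figures rest on more assumptions than the single-score ones.

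**Step 5: what does not change.** The between-group and treatment-by-time tests were identical with IQ centred or not. In a mixed model with IQ as a main effect only, the time estimate and its standard error were also identical: -0.2546 (SE 0.0784) in the worked example, both ways.

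**The case against.** The strongest reply is that the plan never says IQ goes in uncentred. Naming total IQ identifies a score and is not a coding instruction. Centring is routine, and protocols often leave it to the analysis code. The problem also needs IQ to enter the change contrast, and a main-effect-only model escapes it. All of this stands, so the point is conditional and must be worded that way. What it does not remove is that the named method normally carries the covariate into the change contrast, and that a main-effect-only model would leave IQ doing nothing for the test of change.

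A reader might also infer more than the documents support:
- *That the error rate is wrong.* It stays at 0.15 unless IQ predicts change. No section says that it does or by how much. The power loss in Step 2 and the false rejections in Step 3 belong to different scenarios.
- *That the CRT comparisons are compromised.* They are not. The Aim 1 hypothesis in Section 2.1 is comparative, the follow-up ANCOVAs set FBT against a CRT arm, and centring does not touch those tests. A time effect pooled over FBT and CRT could not by itself show that CRT engages the target.
- *That Go/No-Go would be decided wrongly.* Section 6.1 refers to Table 6 for the criteria, and that table is not in the text available. The weight given to the time effect cannot be judged.

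**Conclusion.** The point holds as a gap in specification with a potentially large effect on one of the two kinds of effect Aim 1 reads. It does not establish that the planned analysis is wrong. If IQ is entered as recorded in the standard repeated-measures model, the time test has almost no power for average change (about 0.17 instead of 0.80 at N = 30, one score). If IQ also predicts change at a correlation of .2-.3, it rejects in roughly 35-57% of trials with no average change. Alpha, effect size, correlation between measures and sample size are the plan's. The IQ mean, IQ SD and correlation of IQ with change are assumptions, although the power loss hardly varies over the IQ ranges tried. The correction should be made because it is free and removes an analyst's choice from a result that informs Go/No-Go.

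**What to change.** Replace the covariate sentence in Section 6.1 with wording to this effect: *The covariate is baseline (intake) total WASI IQ, centred at the mean of all randomised persons in the same role (adolescents, mothers, fathers). IQ x time is included in every model. The time effect is reported as the adjusted mean change at average IQ, with its confidence interval.*

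Centring at the role mean gives the omnibus model and the two-arm follow-ups the same reference IQ. Naming the intake score settles which assessment is used and keeps a post-randomisation measurement out of the adjustment. Stating that IQ x time is fitted removes the remaining ambiguity about the model.

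The cost is a few sentences in the plan and one line of code. No data, participants or power are lost, and the between-group and treatment-by-time tests do not depend on the centring.
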